12.3.2 Analysis Methods

This analysis will be a comparison of mortality in 1.5 implanted and non-implanted subjects. Time 0 will be the date of enrollment, and all living subjects will be censored on the last date they were confirmed to be alive.

The analysis, to control for potential imbalance between groups due to not randomizing the subjects to implant or no implant, will include covariates in a Cox proportional hazards model along with implant/no implant as the independent variable. The covariates will include age, sex, country of enrollment, ischemic, LVEF, QRS duration, NYHA, history of syncope, history of NSVT, and history of PVCs. Further baseline covariates or time-dependent covariates may be added in the statistical analysis plan prior to any analysis. ICD/CRT-D will not be a covariate since it will not be known whether non-implanted subjects would have received a CRT-D or not. However, the covariates include all the variables that are commonly used to determine CRT-D use.

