6.8 Quality of Life (QoL) EQ-5D Assessment

The EQ-5D questionnaire will be completed at the baseline visit and at the 6 month follow-up visit for all 1.5 prevention subjects; it is not required for secondary prevention subjects or for subjects that do not meet any of the 1.5 criteria. For this reason, at baseline the EQ-5D questionnaire should be completed after the 1.5 criteria are evaluated. If the EQ-5D questionnaire is skipped, a Study Deviation is required.

This quality of life assessment has five dimensions: mobility, self-care, usual activities, pain/discomfort, and anxiety/depression. Questionnaires will be provided in a language understood by the patient along with instructions for proper administration.

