12.3.1 Hypothesis

Although this is an exploratory objective and is not powered, a hypothesis test will be done and compared to an alpha level of 0.05. To preserve overall type I error, this test is only valid if the primary endpoint is statistically significant.

Compare the mortality rates for patients meeting 1.5 prevention criteria between those implanted with a device (ICD/CRT-D) and those not implanted.

H_0 : Hazard ratio of non-implanted to implanted 1.5 patients = 1

H_A : Hazard ratio of non-implanted to implanted 1.5 patients $\neq 1$

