12.3.3 Power

This objective is not powered and the likelihood of a statistically significant test is not known. So, it should not be a surprise if the endpoint is not statistically significant.

The following table shows what the power of the endpoint would be under various scenarios if doing a log-rank test. It is not known what effect adding covariates in a Cox proportional hazards model will have on the power.

In a retrospective analysis of SCD-HeFT, 1.5 prevention subjects without an ICD had a 25.7% mortality rate at 3 years compared to 18.5% for 1.5 subjects with an ICD. Under the sample size assumptions, it is expected that approximately 430 1.5 subjects will be implanted and 540 will not.

Table 10: Power for 1.5 Prevention Mortality Endpoint

1.5 implanted sample size	1.5 not implanted sample size	Assumed 3-year Mortality				
		26% no ICD	26% no ICD	26% no ICD	22% no ICD	30% no ICD
		18% ICD	20% ICD	22% ICD	14% ICD	22% ICD
450	550	88%	63%	32%	93%	82%
350	650	85%	60%	30%	91%	79%
360	440	80%	53%	27%	87%	73%
350	350	74%	48%	24%	83%	67%

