3.3 Secondary Objective: Mortality

The secondary objective is to compare the mortality rates for patients meeting 1.5 prevention criteria between those implanted with a device (ICD/CRT-D) and those not implanted.

Hypothesis

Although this is an exploratory objective and is not powered, a hypothesis test will be done and compared to an alpha level of 0.05.

H_0 : Hazard ratio of non-implanted to implanted 1.5 patients = 1

H_a : Hazard ratio of non-implanted to implanted 1.5 patients $\neq 1$

Analysis Methods

A Cox proportional hazards model will be used to compare the mortality rates between subjects with device implant and without, in subjects who meet the 1.5 prevention criteria. In addition to the implant/no implant variable, the Cox proportional hazards model will include baseline covariates that are known to be associated with mortality and that might be unbalanced between the groups due to the non-randomized study design. These covariates are:

- age at consent
- sex
- QRS duration
- ischemic cardiomyopathy (yes/no)
- left bundle branch block (LBBB) (yes/no)
- NYHA Classification (treated as an ordinal variable, including 0 for those without HF)
- diabetes (Type 1 or 2 only, gestational not counted) (yes/no)
- LVEF (taken from the 1.5 Visit CRF, if it exists, or from the Baseline CRF)
- syncope qualifying as 1.5 (yes/no)
- NSVT qualifying as 1.5 (yes/no)
- PVCs qualifying as 1.5 (yes/no)

Note that all 3 categorical 1.5 covariates can be found at the end of the 1.5 Criteria CRF. The NSVT and PVC variables on the Baseline CRF do not include the minimum thresholds of 3 consecutive >100 bpm beats for NSVT and 10 or more PVCs per hour.

Country of enrollment was to be included as a covariate according to the CIP, but it will not be included as subjects in the study (who all have medical care) may not have significantly different mortality rates between countries. Also, some countries may have a small number of enrollments. The idea was to have covariates with known mortality risks.

LBBB and diabetes are added covariates from the CIP based on steering committee input. LBBB was added because it is a well-known mortality risk factor. Diabetes was not originally collected in the study, but was added later and is being collected for all subjects, including those enrolled prior to it being added to the Medical History CRF.

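### The mortality model for the non-randomized 1.5 comparison omits baseline EQ-5D, a general-health measure already required in both arms, so avoidable confounding of unknown direction may remain in the implant hazard ratio

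*Protocol*

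**What the plan says.** Protocol 6.9 explains that subjects are not randomized and are asked whether they want a device. Protocol 12.3.2 handles the resulting imbalance with covariates in a Cox model: "The covariates will include age, sex, country of enrollment, ischemic, LVEF, QRS duration, NYHA, history of syncope, history of NSVT, and history of PVCs". The same section lets the SAP add baseline or time-dependent covariates before any analysis.

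SAP 3.3 revises that list, and SAP 3.1.3 says the SAP supersedes the Protocol in some cases. It sets out to include "baseline covariates that are known to be associated with mortality and that might be unbalanced between the groups". Country is dropped; left bundle branch block and diabetes are added on steering committee advice. The result is 11 covariates plus implant status. EQ-5D is not in the list, the imputation model or the sample SAS code, and the visible text gives no reason.

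On collection, Protocol 6.8 states: "The EQ-5D questionnaire will be completed at the baseline visit and at the 6 month follow-up visit for all 1.5 prevention subjects". A skipped questionnaire is a study deviation. The five dimensions are mobility, self-care, usual activities, pain/discomfort and anxiety/depression. Protocol 6.6 and Table 7 confine it to 1.5 subjects, and Protocol 12.3.4 defines the mortality population as the 1.5 cohort at enrollment, so EQ-5D is due in exactly the subjects analyzed.

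The status of the test is modest. Protocol 12.3.1 introduces it with "Although this is an exploratory objective and is not powered", and then says "a hypothesis test will be done and compared to an alpha level of 0.05". The null is "Hazard ratio of non-implanted to implanted 1.5 patients = 1", tested two-sided, and the Protocol treats the test as valid only if the primary endpoint is significant.

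**The concern.** In a comparison formed by patient choice, a covariate-adjusted model is only as good as its covariates. In the SAP list, age, sex and diabetes are general; the rest describe the heart. NYHA class records functional limitation, but nothing records pain, self-care, mood or limitation from other causes. If such aspects of health influence both the decision about a device and the risk of death, and differ between the arms at the same NYHA class, age, LVEF and diabetes status, the implant hazard ratio absorbs the difference.

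At stake is the one secondary objective visible in the documents, which carries a formal 5% test and is intended for the main publication. A measure that could reduce the problem is already collected, but under the current plan it plays no part in that test.

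**Working it through.** **1. The plan's own figure.** Protocol Table 10 gives 88% log-rank power for 450 implanted and 550 non-implanted subjects at 3-year mortality of 18% and 26%.
- Deaths: 450 × 0.18 + 550 × 0.26 = 224.
- Hazard ratio (non-implanted to implanted): ln(0.74)/ln(0.82) = 1.517; its log is 0.417.
- Schoenfeld power: Φ(0.417 × √(224 × 0.45 × 0.55) − 1.96) = Φ(3.10 − 1.96) = 87.4%.

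This agrees with 88%, so the same approximation is used below.

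**2. Precision at the planned size.** From Protocol 12.2.6:
- Implanted 1.5 subjects: 4800 × 0.4 × 0.5 × 0.45 = 432.
- Non-implanted 1.5 subjects: 4800 × 0.4 × 0.5 × 0.55 = 528. Protocol 12.3.3 rounds the groups to 430 and 540: "it is expected that approximately 430 1.5 subjects will be implanted and 540 will not".
- Deaths: 432 × 0.18 + 528 × 0.26 = 215.
- SE of log HR: 1/√(215 × 0.45 × 0.55) = 0.137.

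**3. Illustration of an omitted factor.** The documents give neither the distribution of EQ-5D by implant choice nor its relation to death. Every input here is an assumption, and each is conditional on the covariates already listed. Let poor general health be present in a proportion p1 = 0.20 of implanted and p0 = 0.25 to 0.40 of non-implanted subjects, with mortality hazard ratio g = 1.5 to 2.5 and no ICD effect.
- Apparent HR = (1 + p0(g − 1)) / (1 + p1(g − 1)).
- With d = |ln(apparent HR)| / 0.137, the two-sided rejection probability = Φ(d − 1.96) + Φ(−d − 1.96).

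| p0 v p1 | g | Apparent HR | d | Chance of a significant result |
|---|---|---|---|---|
| 0.25 v 0.20 | 1.5 | 1.125/1.10 = 1.02 | 0.16 | 5% |
| 0.30 v 0.20 | 2.0 | 1.30/1.20 = 1.08 | 0.58 | 9% |
| 0.40 v 0.20 | 2.5 | 1.60/1.30 = 1.23 | 1.51 | 33% |

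The nominal rate is 5%.

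**4. The opposite direction.** Exchange the two prevalences, so that decliners are the healthier group. The apparent HR becomes the reciprocal: 1/1.02 = 0.98, 1/1.08 = 0.92 and 1/1.23 = 0.81. The rejection probabilities are the same, but a significant result now points against the ICD.

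**5. Sensitivity to the death count.** The 215 deaths come from unequal mortality, which does not strictly fit a scenario with no ICD effect. With 25.7% mortality in both arms of 430 and 540, deaths are 970 × 0.257 = 249, the SE is 0.127, and the three chances become 5%, 10% and 37%. The picture does not change.

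**6. Scale.** Protocol 12.3.3 reports that "1.5 prevention subjects without an ICD had a 25.7% mortality rate at 3 years compared to 18.5% for 1.5 subjects with an ICD", which implies a hazard ratio of ln(0.743)/ln(0.815) = 1.45. The apparent ratios in step 3 equal 6%, 21% and 56% of that log hazard ratio.

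**7. Room in the model.** Expected deaths at those rates are 430 × 0.185 + 540 × 0.257 = 218. Eleven covariates, implant status and EQ-5D make 13 parameters, or 218/13 ≈ 17 deaths each. If NYHA is fitted as a class variable with five levels, as the sample code suggests, there are 16 parameters and 218/16 ≈ 14 deaths each. One more covariate is affordable.

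**The case against.** The strongest reply is that this is a modelling preference. The SAP revisited the covariates with its steering committee and gave reasons for each change. Its stated rule is known mortality risk, and no document links EQ-5D to mortality in this population. NYHA class overlaps with mobility and usual activities, and age and diabetes also adjust in part. The magnitude is wholly assumed and its low end is negligible. SAP section 1 expects further analyses anyway, and parts of both documents are redacted, so other planned uses of EQ-5D cannot be seen.

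Much of this stands. That EQ-5D predicts death beyond the listed covariates is a plausible assumption, not something the documents establish, so its omission cannot be called a breach of the SAP's own rule. The partial adjustment is real, which is why the illustration concerns only what remains after it. But a general allowance for additional analyses does not place EQ-5D in the prespecified test, and no visible reason is given for leaving it out.

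A reader might infer that decliners are in poorer health and that the plan is therefore biased toward the ICD. The documents do not support that. All subjects need a Class I indication and no contraindication to a device. The uptake difference that the SAP Appendix does describe is geographic: assumed 1.5 implant rates of 30% in China, 40% in India and 65% elsewhere. People who feel well may also decline. Reasons for refusal are collected (Protocol 6.9.1) and could help settle it.

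**Conclusion.** The point holds as an avoidable gap in confounding control. The operative SAP 3.3 list leaves out a baseline general-health measure that is mandatory in both arms of this comparison, and the Protocol leaves the route open to add it. Residual differences in general health may move the implant hazard ratio either way.

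Under the assumed range, with decliners the less healthy group, the apparent hazard ratio with no ICD effect is 1.02 to 1.23 and the false-positive rate is 5% to 33%; the middle case is 1.08 and 9%. These are illustrations, not estimates, and the upper end needs both assumptions at their extremes.

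The weight is moderate: the objective is exploratory and not powered, the Protocol makes its test depend on the primary result, and the primary endpoint is unaffected. It would go too far to say that the mortality test will show a false ICD benefit.

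**What to change.** Before any mortality analysis, amend SAP 3.3 to:
- Add baseline EQ-5D as one continuous covariate to the 1.5 Cox model and to its imputation model. The sum of the five dimension levels would serve, since it needs no national value set.
- Use only questionnaires dated on or before the implant or refusal decision, and never the 6-month value. The Protocol places baseline EQ-5D after 1.5 testing but does not require it before the decision.
- Report the implant hazard ratio with and without EQ-5D, naming the adjusted model as the one that carries the test.
- Tabulate baseline EQ-5D by implant status, which will show the direction of any imbalance.

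The cost is a short SAP amendment and one more variable in existing code, with no new data collection. There are three small downsides. Some forms will be missing or dated after the decision and must be imputed, and that missingness may depend on how quickly the implant followed. An unweighted level sum may carry reporting differences between countries, which matters because country has been dropped and implant rates are expected to vary by region. The parallel mortality analysis in 1.0 subjects cannot use EQ-5D, because it is not collected there.

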12.3.3 Power

This objective is not powered and the likelihood of a statistically significant test is not known. So, it should not be a surprise if the endpoint is not statistically significant.

The following table shows what the power of the endpoint would be under various scenarios if doing a log-rank test. It is not known what effect adding covariates in a Cox proportional hazards model will have on the power.

In a retrospective analysis of SCD-HeFT, 1.5 prevention subjects without an ICD had a 25.7% mortality rate at 3 years compared to 18.5% for 1.5 subjects with an ICD. Under the sample size assumptions, it is expected that approximately 430 1.5 subjects will be implanted and 540 will not.

Table 10: Power for 1.5 Prevention Mortality Endpoint

1.5 implanted sample size	1.5 not implanted sample size	Assumed 3-year Mortality				
		26% no ICD	26% no ICD	26% no ICD	22% no ICD	30% no ICD
		18% ICD	20% ICD	22% ICD	14% ICD	22% ICD
450	550	88%	63%	32%	93%	82%
350	650	85%	60%	30%	91%	79%
360	440	80%	53%	27%	87%	73%
350	350	74%	48%	24%	83%	67%

12.3.4 Determination of Patients/Data for Analysis

All subjects in the 1.5 prevention cohort at the time of enrollment will be included.

Version 1

13 DATA AND QUALITY MANAGEMENT

Data will be collected and signed and dated by the principal investigator or his/her authorized designee(s) using an electronic data management system for clinical studies. eCRF data will be stored in a secure, password-protected database which will be backed up nightly. Data will be reviewed using programmed and manual data checks. Data queries will be made available to sites for resolution. Study management reports may be generated to monitor data quality and study progress. At the end of the study, the data will be frozen and will be retained indefinitely by Medtronic.

Procedures in the CIP require source documentation. Source documentation will be maintained at the site. Source documents, which may include worksheets, patient medical records, programmer printouts, and interrogation files, must be created and maintained by the investigational site team.

The data reported on the eCRFs shall be derived from source documents and be consistent with these source documents, and any discrepancies shall be explained in writing. In some cases, items on the CRFs may be considered source as long as there is evidence of the visit in the subject's record. Even when the eCRF may be considered as source, an alternate method of source documentation is always strongly encouraged. The eCRF may be considered source for deviations.

Device data from CareLink transmissions will be uploaded to secure servers. Device interrogation files collected via electronic media at office visits will be sent to Medtronic. Upon receipt via transmissions or electronic media, device data will be maintained with databases and retrieved for analysis and reporting.

The sponsor or a regulatory authority may audit or inspect the study site to evaluate the conduct of the study. The clinical investigator(s)/institution(s) shall allow study-related monitoring, audits, Ethics Board review, and regulatory inspection(s) by providing direct access to source data/documents, study related documents, materials, and equipment.

14 WARRANTY/INSURANCE INFORMATION

14.1 Warranty

Warranty information is provided in the product packaging for the commercially released devices and leads; additional copies are available upon request.

14.2 Insurance (Central and Eastern Europe, Middle East and Africa)

Medtronic Bakken Research Center B.V. is a wholly owned subsidiary of Medtronic, Inc., which as the parent company of such entity maintains appropriate clinical study liability insurance coverage as required under applicable laws and regulations and will comply with applicable local law and custom concerning specific insurance coverage. If required, a Clinical Trial insurance statement/certificate will be provided to the Ethics Committee.

14.3 Insurance (India)

India Medtronic Pvt. Ltd is a wholly owned subsidiary of Medtronic, Inc., which as the parent company of such entity maintains appropriate clinical trial liability insurance coverage as required under applicable laws and regulations and will comply with applicable local law and custom concerning specific insurance coverage. If required, a Clinical Trial insurance statement/certificate will be provided to the Ethics Board.

14.4 Insurance (Association of Southeast Asian Nations (ASEAN))

Medtronic International Ltd. is a wholly owned subsidiary of Medtronic, Inc., which as the parent company of such entity maintains appropriate clinical trial liability insurance coverage as required under applicable laws and regulations and will comply with applicable local law and custom concerning specific insurance coverage. If required, a Clinical Trial insurance statement/certificate will be provided to the Ethics Board.

14.5 Insurance (Greater China)

Medtronic (Shanghai) Management Co., Ltd. a wholly owned subsidiary of Medtronic, Inc., which as the parent company of such entity maintains appropriate clinical study liability insurance coverage as required under applicable laws and regulations and will comply with applicable local law and custom concerning specific insurance coverage. As Ethics Committee of local clinical center may have special requirements on the insurance policy or other formal arrangement, it is necessary to provide a Clinical Study insurance statement/certificate to the Ethics Committee for review and obtain favorable opinion.

Medtronic (Taiwan) Ltd. is a wholly owned subsidiary of Medtronic, Inc., which as the parent company of such entity maintains appropriate clinical trial liability insurance coverage as required under applicable laws and regulations and will comply with applicable local law and custom concerning specific insurance coverage. If required, a Clinical Trial insurance statement/certificate will be provided to the Ethics Board.

14.6 Insurance (Korea)

Medtronic Korea Co., Ltd. is a wholly owned subsidiary of Medtronic, Inc., which as the parent company of such entity maintains appropriate clinical trial liability insurance coverage as required under applicable laws and regulations and will comply with applicable local law and custom concerning specific insurance coverage. If required, a Clinical Trial insurance statement/certificate will be provided to the Ethics Board.

14.7 Insurance (Latin America)

Medtronic Logistics LLC is a wholly owned subsidiary of Medtronic USA, Inc., which as the parent company of such entity maintains appropriate clinical trial liability insurance coverage as required under applicable laws and regulations and will comply with applicable local law and custom concerning specific insurance coverage. If required, a Clinical Trial insurance statement/certificate will be provided to the Ethics Committee/Institutional Review Board.

15 MONITORING

It is the responsibility of Medtronic to ensure proper monitoring of this clinical study per regulations. Trained Medtronic personnel or delegates appointed by Medtronic may perform study monitoring at the study site in order to ensure that the study is conducted in accordance with the CIP, the Clinical Trial Agreement, and applicable regulatory and local requirements. Medtronic, or delegates, must therefore be allowed access to the subjects' case histories (clinic and hospital records, and other source data/documentation) upon request as per the Patient Informed Consent, and Clinical Trial Agreement. The consent form or other privacy language where required by law must be available for monitoring and auditing. The principal investigator should also be available during monitoring visits.

15.1 Monitoring Visits

Frequency of monitoring visits may be based upon subject enrollment, duration of the study, study compliance, number of deviations, findings from previous monitoring visits and any suspected inconsistency in data that requires investigation. Regulatory documents (e.g., Ethics Committee approval letters, Clinical Trial Agreements) may be reviewed at each study site. Monitoring for the study, including site qualification visits, site initiation visits, interim monitoring visits, and closeout visits, will be done in accordance to the study-specific monitoring plan.

Monitoring visits may be conducted periodically to assess site study progress, the investigator's adherence to the CIP, regulatory compliance including but not limited to Ethics Committee approval and review of the study, maintenance of records and reports, and review of source documents against subject CRFs. Monitors review site regulatory and study compliance by identifying findings of non-compliance and communicating those findings along with recommendations for preventative/corrective actions to site personnel. Monitors may work with study personnel to determine appropriate corrective action recommendations and to identify trends within the study or at a particular site.

Further details of monitoring will be given in the study monitoring plan.

